5 and word length. Familiarity ratings will be obtained from a normative database. Visual  
6 complexity ratings will be also obtained from a group of 20 individuals using the instructions and  
7 rating scales as reported in Snodgrass and Vanderwart's article. The CELEX database, will  
8 be consulted to determine lexical frequency of the words (cues) used in the study. An additional  
9 40 pictures will be selected for a control (untreated) list that will be used only during baseline  
10 and post-treatment testing. Performance on treated and untreated lists will be compared to  
11 determine treatment effects and possible generalization effects.

12  
13 *Naming Treatment Procedures.* All participants will be provided the same protocol, which will  
14 highlight the process of rehearsing the cues associated with the picture name. Treatment  
15 sessions will last until each participant has gone through the treated items twice. To insure  
16 control during the protocol, a graduate student trained in the protocol will administer the  
17 treatment steps. She will be blinded to the objectives of the study and conditions that are being  
18 administered. Treatment sessions will be video recorded for reliability purposes. To insure that  
19 she is not aware of when tDCS is being administered, a screen will be in place between the  
20 tDCS machine and the treatment table. The protocol is provided in Table 1.

21  
22 **Table 1. Naming Treatment Protocol.**

Steps Involved in Naming Treatment Protocol	
Picture Presentation	Participant will be asked to name the picture. If she/he is unable to provide the name within 10 seconds, the name will be provided.
Cue Presentation	Cues that accompany the picture will be presented. He/she will be asked to read each cue word as it is presented. If he/she is unable to read the word spontaneously within 10 seconds, he/she will be asked to repeat each word after the clinician.
Cue Rehearsal	Both picture and cues are taken away. Participant is asked to rehearse the cue words silently for 10 seconds.
Cue Self-Generation	Participant will be asked to generate all three cues. For each instance that the participant is unable to provide a cue within 10 seconds, the cues will be provided. Once the cues have been provided, the participant will then be asked to provide the picture name.

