26         • a diagnosis of moderate-moderately severe non-fluent aphasia based on  
27         performance on the WAB (see above screening procedures).  
28         • a diagnosis of moderate-moderately severe non-fluent aphasia based on  
29         performance on the BNT (see above screening procedures).  
30         • a diagnosis of mild-moderate apraxia of speech (AoS) based on performance on the  
31         ABA-2 (see above screening procedures).  
32         • completion of high school or GED  
33         • normal or corrected-to-normal vision  
34         • adequate hearing acuity for 1:1 conversational exchanges  
35         • use of English as primary language  
36         • a vascular lesion in the dominant left hemisphere, not in the region of the DLPFC  
37         verified by an MRI scan within six months of the start of the study.

38     These participants must also meet the following exclusionary criteria:

39  
40         • no previous history of neurological- or psychiatric-based illnesses or disease,  
41         language or learning disabilities, or alcohol/substance abuse  
42         • no history of seizures  
43         • no metal implants in the head (except dental fillings)  
44         • no lesion in the left DLPFC confirmed by MRI

1       • no current pregnancy

2  
3 Individuals who meet the inclusionary/exclusionary criteria and who are still interested in  
4 participating will then be consented to participate in the research study. After four  
5 participants have been identified as eligible and consented for the study, recruitment will  
6 stop.

7       • **Are statistical considerations, including sample size and justification, estimated  
8 accrual and duration, and statistical analysis clearly described and adequate to  
9 meet the study objectives?**

10  
11 Descriptive statistics such as naming percent accuracy, range of naming percent accuracy,  
12 number of cues generated independently, and rates of naming errors, will be collected. Although  
13 normally distributed data is not expected in this small sample size and in this population of  
14 participants, a Shapiro-Wilk test of normal distribution will be conducted to report the  
15 distribution. Single subject analysis techniques will be used such as visual inspection, graphical  
16 analysis and confidence interval comparison.

17  
18 *Aim 1.* To address the feasibility and safety aim, the number and type of adverse events for  

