19 each patient will be recorded and presented. In addition, the number of participants who failed  
20 to complete the study will be recorded and factors recorded. To the extent possible, the  
21 participants will be asked to continue to participate in the assessments to allow a consideration  
22 of intent to treat analysis.

23  
24 *Aim 2.* Means and 95% confidence intervals will be plotted and used for comparison of naming  
25 RTs, working memory performance and motor speech performance across treatment conditions  
26 for each subject (Deng, et al. 2013). Naming accuracy performance will be analyzed using  $d'$   
27 statistics for lexical data to determine magnitude of treatment effect. The effect size will be  
28 interpreted using benchmarks proposed by Beeson and Robey (2006) for lexical retrieval  
29 treatments: small ES = 4.0, medium ES = 7.0, large ES = 10.1. Naming RT mean and  
30 confidence intervals will be analyzed for changes within and across treatment conditions using  
31 visual inspection.

32  
33       • **Are all the proposed tests or measurements requested necessary to answer the  
34 scientific question?**

35 Yes. The proposed measures will allow investigators to report the feasibility and safety of  
36 the use of a-tDCS. The measures will also allow investigators to identify individual treatment  
37 effects of a-tDCS to left DLPFC combined with behavioral naming therapy on naming in non-  
38 fluent aphasia and through visual inspection and graphical analysis, compare effects to sham  
39 treatment. Naming RT and accuracy are sensitive measures of the participant's retrieval and  
40 learning of treated items. Motor speech performance will allow us to track changes in motor  
41 planning and sequencing abilities, which can influence naming RT and naming accuracy.  
42 And, performance on working memory tasks will allow for investigation of the influence of  
43 WM on naming and to provide additional evidence that a-tDCS to the left DLPFC may  
44 influence WM in individual participants.

45  
46       • **Are the investigators well qualified to conduct this study?**

47  
48 **Key Personnel**

1                   **Name**

2                   [name] CCC-SLP

3                   **Affiliation**

4                   University Wisconsin River Falls

5                   **Role**

6                   PI

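### For naming RT, working memory and motor speech, investigators who know which block is REAL judge the graphs by eye with no stated criterion

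*Combined protocol and SAP*

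**What the plan says.** The section on statistical considerations sets the general approach: "Single subject analysis techniques will be used such as visual inspection, graphical" analysis and comparison of confidence intervals. Its Aim 2 paragraph then divides the outcomes.

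- **Naming RT, working memory, motor speech.** "Means and 95% confidence intervals will be plotted and used for comparison of naming" RTs, and of the other two outcomes, across conditions for each subject. For RT the paragraph adds that means and "confidence intervals will be analyzed for changes within and across treatment conditions using" visual inspection.
- **Naming accuracy.** A d' statistic gives the magnitude of the treatment effect, read against published benchmarks for lexical retrieval: "treatments: small ES = 4.0, medium ES = 7.0, large ES = 10.1".

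The later section on whether the proposed measurements are necessary says that the measures let the investigators identify individual effects and, in a phrase covering the measures as a whole, "fluent aphasia and through visual inspection and graphical analysis, compare effects to sham" treatment.

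Masking is described under Naming Treatment Procedures. It concerns the graduate student who delivers the "treatment steps. She will be blinded to the objectives of the study and conditions that are being" administered, with a screen hiding the stimulator. The section on validity and reliability adds point-by-point agreement for treatment steps and for naming error types.

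**The concern.** For three of the four outcome families, the comparison with sham ends in someone looking at a plot and deciding. The plan does not say what that person must see before calling a difference. The people who look have a directional hypothesis: improvement after REAL, none after SHAM. Because every participant has the same sequence, a plot in time order reveals the condition even if no label is printed on it.

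Some panels may be unclear. A reader who expects REAL to be better can settle those in one direction across all four participants, and so produce a consistent pattern without any stimulation effect. Masked scoring of the probes would not prevent this, because the judgement comes after scoring. The consequence reaches beyond this study: Aim 2 is also meant to establish a sample size for future work, and the findings are described as the foundation for a larger trial.

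**Working it through.** The plan states no alpha, power, standard deviation or decision rule, so there is no figure to reproduce. The main check sets the sections side by side.

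1. **How is the comparison made?** By plotted means and 95% confidence intervals, read by eye (statistical considerations, Aim 2). No overlap rule, test or count of participants is given. Nor is it said whether an interval is taken over sessions or over items.
2. **Who makes it?** The section on necessary measurements names the investigators. No independent or masked reader is mentioned.
3. **What do they know?** The sequence is SHAM then REAL for everyone (Treatment Design), and the expected direction is written down (Hypothesis 2).
4. **What do the safeguards cover?** Therapy delivery is masked. Agreement is checked for treatment steps and error types. Neither applies to graph reading.
5. **How many judgements are there?** Recruitment stops at four participants, so there are four pairs of blocks per outcome.

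The arithmetic below shows only how results depend on assumptions that the documents do not supply.

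**Illustration A: a forced-choice reader who leans to REAL.** Let z be the REAL-SHAM difference in standard errors, distributed N(0,1) when there is no effect. The reader gives every pair with |z| < b to REAL and reads the rest correctly. Then p = P(|z|<b) + [1 − P(|z|<b)]/2, and the chance that REAL is called better in all four participants is p⁴.

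| b | P(\|z\|<b) | p | p⁴ |
|---|---|---|---|
| 0 | 0 | 0.500 | 0.0625 |
| 0.25 | 0.197 | 0.599 | 0.128 |
| 0.5 | 0.383 | 0.691 | 0.229 |
| 1 | 0.683 | 0.841 | 0.501 |

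**Illustration B: an assumed share u of unclear panels, all read towards REAL.** Here p = u + (1 − u)/2. For u = 25%, 50% and 75%, p is 0.625, 0.75 and 0.875, and p⁴ is 0.153, 0.316 and 0.586.

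**Is 1/16 a valid chance reference for a masked reading?** It equals 0.5⁴ and needs a forced choice and no order effect. Neither condition holds.

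- If an unbiased reader may answer *neither* when |z| < 0.5, the chance of choosing REAL in a pair is P(z > 0.5) = 0.3085. Four of four then has probability 0.3085⁴ = 0.009, or 0.9%.
- If the second block gains 0.5 standard errors from practice, order or list alone, a perfectly masked forced-choice reader picks REAL with probability P(z > −0.5) = 0.691. Four of four then has probability 0.691⁴ = 0.23, or 23%.

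The second result matches the b = 0.5 row of Illustration A. A count of panels favouring REAL therefore cannot by itself tell reader bias from an order effect.

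**The case against.** The best defence is that the plan does not rely on impression alone. Confidence intervals are drawn, naming accuracy has a numerical d' with fixed benchmarks, and no pooled test or four-of-four rule is planned. The primary purpose is feasibility and safety in four people, so masked graph reading is a refinement. The fixed order and the missing decision rule are more basic.

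Much of this stands, and it limits the point in three ways where a reader might infer more.

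- **That the whole REAL-SHAM comparison is made by eye.** The documents do not support this. Naming accuracy has its own statistic. It is less exposed, though not fully protected: the benchmarks grade a treatment effect, and no rule compares d' under REAL with d' under SHAM.
- **That the bias is about 23% or 50%.** These figures belong to an assumed reader who must name a winner and gives REAL even those close pairs where the SHAM mean is slightly better. The plan forces no choice, and with overlapping intervals the natural call may be no difference. Nor do the documents show that most panels will be unclear.
- **That masking would make chance agreement known, at 1/16.** It would not, for the two reasons worked out above.

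What the defence does not answer is that an interval on a plot is not a criterion, and that nothing hides the condition from those who apply their judgement. Some pages around the personnel listing are not in the text available. A masked reader named there would answer the masking part of the point.

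**Conclusion.** The point holds for naming RT, working memory and motor speech. The comparison with sham rests on investigators viewing plotted means and intervals without a stated criterion, knowing that REAL is the second block and expecting it to be better. The plan's masking and agreement checks stop short of this step, so unclear panels can be read towards Hypothesis 2.

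The direction of the possible bias is clear; its size is not derivable. It would depend on how many panels are unclear and how they are read, and the documents give neither. The illustrations should not be quoted as an expected effect.

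This is a worthwhile, cheap improvement, not a flaw that invalidates the study. It does not affect Aim 1.

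**What to change.** Add a masked reading procedure to the Aim 2 paragraph for naming RT, working memory and motor speech.

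1. **State the baseline.** Plot each block as change from a named baseline. For RT, say whether the list 2 baseline is the measurement before SHAM or the one after washout, since both exist. Working memory and motor speech have no word list, so name the pretreatment measurements used.
2. **Hide the condition.** Keep session order within each block, remove dates, list and condition labels, and show the blocks as A and B in random order. Removing labels alone is not enough, because time order identifies REAL.
3. **Write the criterion beforehand.** One example is non-overlap of the plotted intervals, which also requires saying what each interval is taken over.
4. **Read independently.** The investigator and co-investigator each record on a form whether each block shows improvement and whether A, B or neither shows more, before the key is opened.
5. **Report descriptively.** Give both readers' calls and their agreement. Do not print 1/16 as a chance probability.

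The cost is a plotting script and a short form, with no extra patients or staff. There are three drawbacks. Masking may be incomplete: there are only four participants, and the co-investigator observes about 20% of each participant's treatment sessions, so the readers may recognise the data. Trends across blocks can be viewed only after the masked reading. And the procedure removes reader bias alone, leaving the confounding of condition with order untouched.
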